7.4.1 Analysis of Co-primary Endpoint

7.4.1.1 Co-primary Analysis

The 4 co-primary efficacy endpoints are the mean change in the frequency of moderate to severe VMS and the mean change in severity of VMS (per 24 hours) from baseline to week 4 and week 12.

For each of the 4 co-primary efficacy endpoints, a mixed models repeated measures analysis of covariance (MMRM) will be used with treatment group, week and smoking status (current vs former/never) as factors, with baseline weight and baseline measurement as covariates, as well as an interaction of treatment by week and an interaction of baseline measurement by week. An unstructured covariance structure shared across treatment groups will be used to model the within-patient errors. The Kenward-Roger approximation will be used to estimate denominator degrees of freedom and adjust standard errors. This analysis will use a restricted maximum likelihood-based repeated-measures approach. The treatment difference will be estimated at all study weeks. MMRM will use all available on-treatment data to inform mean treatment effect estimates without requiring explicit imputation for missing data (i.e., for discontinued subjects). This approach is consistent with the hypothetical strategy used for the estimand, which is to compare patients as though they had continued on the assigned treatment.

Comparisons between the fezolinetant and placebo will be calculated based on least-squares mean contrasts using a 2-tailed 95% confidence interval (CI).

The hypothesis for each pairwise comparison is given as follows:

H0: The change from baseline at week 4 (or 12) for fezolinetant and placebo are the same

H1: The change from baseline at week 4 (or 12) for fezolinetant and placebo are not the same

The co-primary analysis will use the FAS.

Frequency of moderate or severe VMS events will be calculated as the sum of moderate or severe VMS events per day.

Severity of post-baseline co-primary severity endpoints will be calculated using a weighted average defined as shown below. Note that the calculation for severity at baseline uses a similar formula, but does not include mild VMS events in the numerator or denominator.

$$\frac{([\text{number of mild hot flashes/day} \times 1] + [\text{number of moderate hot flashes/day} \times 2] + [\text{number of severe hot flashes/day} \times 3])}{\text{total number of daily (or weekly) mild/moderate/severe hot flashes}}$$

Daily frequency and severity per week (e.g., week 4, week 12) will be calculated as the average frequency or severity over 7 days. The specific windows will be defined in the SAP.

The family-wise type I error rate for the 2 active dose groups compared to placebo for the 4 co-primary efficacy endpoints will be controlled using a Hochberg approach. All 4 co-primary endpoints must be statistically significant for a given dose to be considered successful. Given that, the largest p-value from the 4 co-primary endpoints in each dose group will be used to test that dose because it represents the least significant of the co-primary endpoints. If the larger of the 2 maximum P values, one from each dose, is less than 0.05, then both dose groups are considered statistically significant. If not, then if the smaller of the P values is less than 0.025, the second compared dose is considered statistically significant. Otherwise, neither dose is considered statistically significant. The trial will be considered successful if at least one dose is statistically significant.

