5 ENDPOINTS

The calculation of efficacy baseline for VMS frequency and severity is described in the 12-week analysis SAP, and will be calculated based on the number of moderate to severe hot flashes in the 10 days immediately prior to randomization.

For general efficacy endpoints collected at visits, the last non-missing assessment on or prior to the first dose of study treatment (investigational product or placebo) is the baseline.

For all general safety endpoints, in contrast, the baseline value will be the last non-missing value taken on or prior to first dose of fezolinetant.

Note that the baseline calculations differ between efficacy and safety analyses. The efficacy endpoints are subjective and there is expected to be a non-ignorable placebo effect, so the entire double-blind portion of the study is considered post-baseline for all subjects. For safety endpoints, any changes while on placebo during the double-blind portion of the study are expected to be within-subject variation and changes from baseline will be assessed beginning with exposure to fezolinetant.

The table below provides additional details regarding the baselines for specific endpoints. The terms R_{BL} and $WK12_{BL}$ indicate where the baseline is established, where R_{BL} is initial randomization and $WK12_{BL}$ is the start of the extension period at Week 12.

| Endpoint | Baseline | | |
|--|-----------------|-----------------|--|
| - | fezolinetant / | placebo / | |
| | fezolinetant | fezolinetant | |
| General efficacy | R _{BL} | R _{BL} | |
| General safety and TVU | R _{BL} | $WK12_{BL}$ | |
| Hormones | R _{BL} | $WK12_{BL}$ | |
| Demographics | R _{BL} | R_{BL} | |
| Medical history | R _{BL} | R _{BL} | |
| Prior medications | R _{BL} | $WK12_{BL}$ | |
| Concomitant medications | R _{BL} | $WK12_{BL}$ | |
| Study drug exposure and compliance | R _{BL} | $WK12_{BL}$ | |
| TEAE | R _{BL} | $WK12_{BL}$ | |
| Clinical lab summary shifts and liver safety assessments | R _{BL} | $WK12_{BL}$ | |
| Protocol deviations | R _{BL} | R _{BL} | |
| Biopsy (Listing only) | R _{BL} | R _{BL} | |

The 12-week double-blind placebo period will be completely described as part of the treatment comparisons within the 12-week double-blind analyses. As a result, all endpoints in the 52-week analysis are from the first dose of fezolinetant and onward (see Section 6.10 for additional details).

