5.2.2 Secondary Endpoints

The secondary efficacy objectives that extend beyond the double-blind treatment period and examine the effect of fezolinetant over time are the following:

- Mean change in the frequency of moderate to severe VMS from baseline to week 24 (descriptive)
- Mean change in the Severity of moderate to severe VMS from baseline to week 24 (descriptive)

These will be described as a time point of particular interest within the exploratory VMS endpoint below.

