Severity of post-baseline co-primary severity endpoints will be calculated using a weighted average defined as shown below. Note that the calculation for severity at baseline uses a similar formula, but does not include mild VMS events in the numerator or denominator. The calculation of baseline and post-baseline severity is based on specific direction from the FDA during the Type B end-of-phase 2 meeting of April 17, 2019. This calculation allows for the capture all hot flashes on treatment, including mild.

([number of mild hot flashes/day \times 1] + [number of moderate hot flashes/day \times 2] + [number of severe hot flashes/day \times 3]) / total number of daily mild/moderate/severe hot flashes

At baseline, severity is zero for any individual days on which subjects have zero moderate or severe symptoms. Severity for post-baseline individual days is zero for subjects who have zero mild, moderate or severe vasomotor symptoms.

At baseline, as mentioned at the start of Section 5 frequency and severity are based on the non-missing values in the 10 days immediately prior to randomization. After baseline, daily frequency and severity for specific weeks (e.g., week 4, week 12) will be calculated as the average over non-missing days over 7 days period. Days without any reporting of VMS events will be considered missing for that day. For both post-baseline frequency and severity, a daily average per week will be derived if any information for 4 or more days was reported.

All 4 co-primary endpoints must be statistically significant for a given dose to be considered successful. Details regarding determination of statistical significance are provided in Section 6.4

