5.2.2 Secondary Endpoints

The secondary efficacy objectives examine the effect of fezolinetant versus placebo on the following:

- Mean change in the frequency of moderate and severe VMS from baseline to each week up to week 12
- Mean change in the severity of moderate and severe VMS from baseline to each week up to week 12
- Mean percent reduction in the frequency of moderate and severe VMS from baseline to each week up to week 12
- Percent reduction ≥ 50% and at 100% in the frequency of moderate and severe VMS from baseline to each week up to week 12
- Mean change in the frequency of moderate to severe VMS from baseline to week 24 (descriptive) [Analysis to be described in the 52-Week SAP]
- Mean change in the Severity of moderate to severe VMS from baseline to week 24 (descriptive) [Analysis to be described in the 52-Week SAP]
- Score on the Patient Global Impression of Change (PGI-C) in VMS at each visit

The severity of moderate to severe VMS for all secondary endpoints in this Section will be calculated as described in Section 5.1 where baseline severity include moderate and severe VMS events, while post-baseline severity includes mild, moderate and severe VMS events in the calculation.

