5.3.1 VMS events

Exploratory endpoints that include mild post-baseline VMS events (frequency, severity, percent reduction, and responder analyses) also consider mild VMS at baseline.

The severity of moderate to severe VMS in this Section will be calculated as described in Section 5.1 where both baseline and post-baseline severity include only moderate and severe VMS events in the calculation.

For the daily frequency of moderate and severe VMS endpoint, the baseline frequency and post-baseline daily frequency will be calculated as described in Section 5.1 In addition, the co-primary endpoints will also be re-derived excluding data affected by COVID-19.

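### Severity is scored without mild VMS at baseline but with them afterwards; in the uncontrolled 52-week output this puts a definitional shift into the Week 24 change, and the formula for the other extension visits is not stated

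*Protocol*

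**What the plan says.** **The formula.** After baseline, mild, moderate and severe events are weighted 1, 2 and 3 and divided by the count of all three (12-week SAP 5.1: "Severity of post-baseline co-primary severity endpoints will be calculated using a weighted average defined as shown below"). The baseline score uses the same weights but "does not include mild VMS events in the numerator or denominator" (Protocol 7.4.1.1, repeated in 12-week SAP 5.1). The 12-week SAP says the FDA directed this at the end-of-phase 2 meeting and gives the reason: "This calculation allows for the capture all hot flashes on treatment, including mild". It also sets a zero rule: "At baseline, severity is zero for any individual days on which subjects have zero moderate or severe symptoms".

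**To Week 12.** There is a concurrent placebo arm. Two symmetric exploratory versions are also planned. One counts mild events at both times (12-week SAP 5.3, 5.3.1). The other is the version "where both baseline and post-baseline severity include only moderate and severe VMS events in the calculation" (5.3.1, analysed in 6.4.4).

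**After Week 12.** The 52-week SAP takes its diary endpoints from the 12-week SAP (section 5). It says that baseline for frequency and severity "will be calculated based on the number of moderate to severe hot flashes in the 10 days immediately prior to randomization", but it gives no post-baseline severity formula. Change in severity at Week 24 is a descriptive secondary endpoint (5.2.2), reported inside the exploratory output for every extension visit and follow-up (5.3, 6.4.2). All four groups receive fezolinetant and nothing is compared (6.1). The only planned repeat of the VMS summary drops diary data affected by COVID-19 (6.4.1).

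**The concern.** Where there is no placebo group, the within-group change from baseline is the result that a reader sees. If baseline is scored without mild events and the later visit with them, part of the change comes from the definition. A woman with some mild events whose diary is the same before and after is recorded as having less severe symptoms.

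Up to Week 12 the reader has two protections: the placebo arm and the symmetric versions. Neither carries over. The 52-week SAP also excludes post-baseline data from before the first fezolinetant dose (section 5, 6.10.1), so no placebo column appears even for the early weeks.

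**Working it through.** **1. Which rule applies after Week 12.**
- *Week 24.* 12-week SAP 5.2.2 lists Week 24 severity among the secondary endpoints. For all of them it uses a moderate/severe baseline, "while post-baseline severity includes mild, moderate and severe VMS events in the calculation". Week 24 is therefore asymmetric.
- *Other extension and follow-up visits.* These are exploratory (12-week SAP 5.3). Section 5.3.1 says that severity in its section is symmetric. However, the extension bullet in 5.3 has no pointer to 5.3.1, while the moderate/severe-only bullet does. The 52-week SAP then reports Week 24 within this same output. The rule is open.

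**2. The plan's own severity figure, for scale.** Protocol 7.1 gives 79% power for a difference of -0.40 (SD 1, 120 per arm, two-sided alpha 0.025). The two-sample t calculation gives 80.0%, and 120/(1 - 0.20) = 150 per arm. Both reproduce adequately, and the present point does not affect them.

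**3. The shift for an unchanged diary.** Let S0 be her moderate/severe severity and p the mild share of all her events.
- Baseline score: S0.
- Post-baseline score: p × 1 + (1 - p) × S0.
- Change: -p(S0 - 1).

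**4. Worked cases (assumed diaries).**
- 10 moderate and 5 mild per day: baseline 20/10 = 2.00; later (20 + 5)/15 = 1.67; change -0.33.
- 3 mild, 5 moderate, 3 severe: baseline 19/8 = 2.375; later 22/11 = 2.00; change -0.375.
- 6 moderate and 4 severe (S0 = 2.40) with 0, 1, 2, 3 or 4 mild: change 0.00, -0.13, -0.23, -0.32 or -0.40. Simulated Poisson diaries (10 baseline days, 7 later days) gave the same means to within 0.001. Under either symmetric definition the mean change was 0.00 to within 0.001.

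**5. Range.** The documents give no mild share and no baseline severity, so both are assumed:

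| S0 | p = 10% | p = 20% | p = 30% |
|---|---|---|---|
| 2.2 | -0.12 | -0.24 | -0.36 |
| 2.4 | -0.14 | -0.28 | -0.42 |
| 2.6 | -0.16 | -0.32 | -0.48 |

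**6. Randomized comparison.** With the same diary process in two arms of 120 (mild rate varying between women, mean 2 per day; 6 moderate and 4 severe), a t-test on the asymmetric change rejected in 5.2% of 4,000 null trials at a nominal 5%. The shift cancels between arms.

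**The case against.** **The extension visits may already be symmetric.** Taken literally, 12-week SAP 5.3.1 covers them. This stands: a reader might infer that the asymmetric formula governs every extension visit, but the documents settle that only for Week 24. The missing pointer and the merged output leave the rest ambiguous, which is itself a reason to state the formula.

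**The formula was directed, and the co-primary tests are sound.** Both are true. A reader might infer that the asymmetry undermines the Week 4 and Week 12 tests. It does not: under the null both arms carry the same shift.

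**Mild events at baseline do not enter the score.** Correct. A reader might infer that every woman with mild VMS at baseline shows an automatic fall. The shift depends on the mild share after baseline and is zero if there are no mild events. It reverses for days with only mild events, which score 0 at baseline and 1 later. Such baseline days should be rare, given an entry minimum of 7 to 8 moderate to severe events per day.

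**Persistence of effect is not distorted.** This also stands where the visits share one formula. Comparing Week 12 with Week 24 or Week 52 is then unaffected by the baseline definition, so the documents do not support saying that the formula manufactures a sustained effect.

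**The -0.40 yardstick is not like for like.** Agreed: it is a planned between-arm difference, while the shift is within-woman. It serves only as a sense of scale.

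**These results are labelled descriptive.** They are, and no test uses them. Week 24 severity is still a named secondary endpoint, and a descriptive change should not mix two definitions without saying so.

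**Conclusion.** The point holds in a limited form. At Week 24 the 52-week severity change from baseline contains a definitional component of -p(S0 - 1), with no placebo group and no symmetric summary to show its size. The same is true of the other extension and follow-up visits if the asymmetric rule is meant there. In that case a woman with mild events who returned exactly to her baseline diary after stopping treatment would still show an improvement at follow-up.

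Under the assumed shares and baseline severities the component is between -0.12 and -0.48; the true mild share is unknown. It bears on the size of change from baseline only. The co-primary tests, the power and the success criterion are untouched. This is a cheap improvement, not a flaw in the trial's main conclusion.

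**What to change.** In 52-week SAP 5.2.2, 5.3, 6.4.1 and 6.4.2:

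- State which severity formula applies at Week 24 and at each extension and follow-up visit.
- Beside the directed version, add a symmetric descriptive summary of change in severity at those visits. Use the version that counts mild events at both times (12-week SAP 5.3), the moderate/severe-only version (5.3.1), or both. If the first is used, the baseline sentence in 52-week SAP section 5 needs a matching clause, because it covers moderate to severe events only.
- Leave the co-primary definition and analysis unchanged.

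The cost is one or two extra descriptive tables, from derivations that the 12-week SAP already defines, and more than one severity figure to explain. The two symmetric versions are not interchangeable. The moderate/severe-only score gives no credit for shifts from severe to mild: 10 severe events becoming 1 severe and 9 mild stays at 3.0. The version with mild events at both times moves from 3.0 to (9 × 1 + 1 × 3)/10 = 1.2. If only one is added, that difference should guide the choice.

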7.4.1.2 Sensitivity Analysis of Co-primary Endpoints

Sensitivity analyses will be carried out for the co-primary efficacy endpoints based on the PPS populations. The data will be analyzed using the same MMRM model as the primary analyses, but the comparison of interest is a particular week within each population (week 4 when using PPS4, and week 12 when using PPS12).

The analysis for each of the co-primary endpoints also will be conducted using a simplified MMRM model with treatment group and week as factors, with baseline measurement as a covariate, as well as an interaction of treatment by week and baseline by week.

7.4.1.3 Subgroup Analysis

The simplified MMRM for the co-primary efficacy endpoints analyses will be repeated, including but not limited to, smoking status, body mass index and race.

7.4.2 Analysis of Secondary Endpoints

The analysis of secondary efficacy endpoints will be based on the FAS. For efficacy endpoints collected at visits, the last non-missing assessment prior to the first dose of study treatment (investigational product or placebo) is the baseline.

7.4.2.1 Key Secondary Endpoint

The PROMIS SD SF 8b scale will be analyzed using MMRM, similar to the primary analysis of the co-primary endpoints.

If all the co-primary endpoints are statistically significant between fezolinetant and placebo at both doses, then the 5% alpha from the analysis of the co-primary endpoints will be passed to the key secondary endpoint as part of the family-wise error rate.

7.4.2.2 Secondary Endpoints

For percent reduction at weeks 4 and 12, an MMRM model as described in [Section 7.4.1.1 Co-Primary Analysis] will be used. Additional calculations of severity will be described in the SAP and will also be analyzed as described in Section 7.4.1.1 Co-Primary Analysis.

For each of the secondary responder endpoints, logistic regression will be used for the analysis for each week and endpoint. A missing value will be imputed as a nonresponder.

PGI-C will be analyzed using Cochran Mantel Haenszel test.

7.4.3 Analysis of Exploratory Endpoints

Percent reduction, PROMIS (SD and SRI total scores), MENQOL total, EQ-5D domain scores and WPAI-VMS total score will be assessed using an MMRM model as described in [Section 7.4.1.1 Co-Primary Analysis]. Percent reduction and absolute reduction will be analyzed as described for the secondary responder endpoints. PGI-S will be analyzed using Cochran Mantel Haenszel test adjusted for baseline score. The median change in serum concentrations of sex hormones and sex hormone-binding globulin (SHBG) from baseline to weeks 4 and 12 and the mean change in serum concentrations of BSAP, P1NP and CTX from baseline to week 12 will be summarized.

NOTE: Assessments after the 12-week placebo-controlled period are descriptive only, because there is no placebo control.

7.5 Analysis of Safety

Safety will be assessed by examining the incidence of AEs, physical examinations findings, the clinician-administered C-SSRS, TVU's, endometrial biopsies, vital signs, ECGs, clinical laboratory tests and bone marker concentrations over time.

7.5.1 Adverse Events

AEs will be coded using MedDRA.

TEAE is defined as an AE observed after starting administration of the study drug and 21 days after the last dose of study drug.

The number and percentage of subjects with treatment-emergent AEs, SAEs, AEs leading to withdrawal of treatment and AEs related to study drug will be summarized by system organ class, preferred term and treatment group. The number and percentage of AEs by severity will also be summarized.

A study drug-related TEAE is defined as any TEAE with a causal relationship of YES by the investigator.

7.5.2 Laboratory Assessments

For quantitative laboratory measurements descriptive statistics will be used to summarize results and change from baseline for subjects in the SAF by treatment group and time point.

Shifts relative to normal ranges from baseline to each time point during treatment period in lab tests will also be tabulated. Laboratory data will be displayed in listings.

The liver safety assessments will be summarized by the categories below based on the measurements from alkaline phosphatase (ALP), ALT, TBL, AST and their combination. These parameters will be based on measurements from a central laboratory.

The subject's highest value during the treatment period will be used.

- ALT > 3 × ULN, > 5 × ULN, > 10 × ULN, > 20 × ULN
- AST > 3 × ULN, > 5 × ULN, > 10 × ULN, > 20 × ULN
- ALT or AST > 3 × ULN, > 5 × ULN, > 10 × ULN, > 20 × ULN
- ALP > 1.5 × ULN
- TBL > 2 × ULN
- (ALT or AST > 3 × ULN) and TBL > 2 × ULN
- (ALT or AST > 3 × ULN) and ALP < 2 × ULN and TBL > 2 × ULN

The last 2 criteria where 2 or more parameters are evaluated will be with the measurements on the same day or up to 1 day apart.

7.5.3 Vital Signs

Descriptive statistics will be used to summarize vital sign results and changes from baseline for subjects in the SAF by treatment group and time point.

7.5.4 Physical Examination

Physical examination will be listed by treatment group.

7.5.5 Routine 12-lead Electrocardiograms

The 12-lead ECG results will be summarized by treatment group and time point.

All ECG interpretations will be displayed in listings.

7.5.6 Endometrial Health Assessment

Data collected based on endometrial biopsy and endometrial thickness from transvaginal ultrasound images will be summarized by treatment group and time point.

